- 2) Physicians who have experienced anti-TNF α antibody treatment to patients with Crohn's disease ^{*2}

^{*1} This condition will be used during the all-case investigation of Humira in Crohn's disease

^{*2} This requirement will be used after the conditions for approval were completely removed.

6. Methods of the investigation

(1) Principles of the investigation

Patients who receive Humira in the applicable institutions (that satisfy the criteria for institutions and physicians and have concluded agreements with AbbVie GK.) will be registered using a central registration method.

(2) Procedures for requesting cooperation and concluding agreements

- 1) Medical representatives will provide investigators and other healthcare professionals with a complete set of informational materials on safety measures (for physicians expect the investigators participating in the all-case investigation), and will inform them about the characteristics of Humira, the purpose of the investigation, patients to be investigated, and methods of investigation.

(3) Procedures of the investigation

- 1) A paper-based case report form (CRF) will be used to collect investigation data.
- 2) Each patient will be observed during 3 years after the onset of Humira treatment.
- 3) When the treatment with Humira is selected for a patient who has expressed his/her consent for treatment, the investigator will fill out a registration form without delay* and submit it to the registration center to register the patient.
- * Basically, we accept registration forms with a postmark date within 14 days after the date of first administration of Humira (the first treatment date is Day 0).
- 4) Investigators will fill out the CRF for each patient every 6 months for 3 years after the initiation of Humira treatment, and provide it to a medical representative (MR). Accordingly, a total of 6 copies of CRFs will be obtained for each patient. When a patient discontinues Humira treatment during the investigation period, the investigator will fill out the CRF for the patient without delay at the time of discontinuation of treatment, and provide it to a MR.
- 5) The sponsor (AbbVie GK.) will confirm the contents of the registration form and CRFs, and perform reinvestigation whenever necessary.

(4) Adverse Event Reporting

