In the event of a serious adverse event, and additionally, any non-serious events of malignancy in patients 30 years of age and younger, whether related to adalimumab or not, if applicable - the physician will notify the AbbVie contact person (Medical Representative in Japan) within 24 hours of the physician becoming aware of the event.

7. Duration of the investigation

Registration period: November 2011 ~ October 2013

Investigation period: November 2011 ~ March 2017

<Milestones>

Major study milestones and their planned dates are as follows:

Start of Data Collection: November 2011

Registration in the EU PAS register: Not Applicable

End of Study: The date on which statistical analysis dataset for

8. Items to be investigated

(1) Observation period

Patients will be observed for 3 years after the initiation of Humira treatment. (Patients who will continue Humira treatment for more than 3 years will also be evaluated at the end of third year to enable completion of the CRF). Patients who have been lost to follow-up during the observation period due to transfer to another hospital, discontinuation of treatment* or for other reasons will be handled as cases of discontinuation of the survey.

* A patient who has suspended Humira treatment for at least 2 months should be considered a case of discontinuation of Humira treatment that will be handled as a case of discontinuation of the survey.

(2) Registration form

Name of institution, date of completion of the registration form, name of department, name of investigator, patient ID, patient's birthdate (year/month) or age, sex, presence/absence of pregnancy/lactation (for female patients), reasons for use of Humira, date (or planned date) of initiation of Humira treatment, contraindications to use of Humira, conditions requiring special care in administration, presence/absence and effectiveness of previous treatment of Crohn's disease, history of biological therapy, presence/absence of tuberculosis or other infection (tuberculin skin test, Quantiferon test, chest X-ray, and chest CT), hepatitis B virus test (HBs antigen test), presence/absence of preventive anti-tuberculosis treatment, and baseline laboratory data (blood β-D-glucan level, peripheral blood WBC, and peripheral blood lymphocyte count).

(3) Data to be collected via CRF

1) Patient background

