Smoking history, in/outpatient, past and current history of Crohn's disease, height, weight, duration of illness, complications, past illnesses, and history of allergy.

2) Previous anti-TNF α treatment of Crohn's disease

Presence/absence, history, and reasons for discontinuation of anti-TNF α treatment.

3) Previous drug treatment of Crohn's disease (treatment during the 3-month period prior to the investigation)

Presence/absence and contents of previous treatment of Crohn's disease

4) Treatment with Humira

At the time of first administration: method of administration, initial dose, and date of initial administration.

At the second administration: method of administration, dosage, and date of second administration

At the third administration and thereafter: method of administration, dosage, interval of administration, duration of administration, and reasons for change in dose or interval of administration.

Patients performing self-injection: presence/absence of written consent for transition to

self-injection, and presence/absence of self-injection transition record.

5) Treatment with antituberculosis agents

Presence/absence of antituberculosis agents, names of drugs, daily dose, and duration

6) Status of administration of concomitant drugs

Presence/absence of concomitant drug use for Crohn's disease, name of drug, route, dose, and duration.

7) Usage of non-drug treatment for Crohn's disease

Presence/absence and type of non-drug treatment, and duration.

8) Presence/absence of development of tuberculosis or serious infections

Day of examination, imaging technique, presence/absence of abnormal laboratory findings, and description of abnormal findings.

9) Crohn's Disease Activity Index (CDAI)

Evaluate at baseline and week 4, month 3, month 6, year 1, year 1.5, year 2, year 2.5 and year 3 of Humira treatment, and at the time of discontinuation of the treatment

10) Work Productivity and Activity Impairment Questionnaire: Crohn's disease (WPAI: CD)

Evaluate at baseline and week 4, month 3, month 6, year 1, year 1.5, year 2, year 2.5 and year 3 of Humira treatment, and at the time of discontinuation of the treatment.

11) C-reactive protein (CRP)

Evaluate at baseline and week 4, month 3, month 6, year 1, year 1.5, year 2, year 2.5 and year 3 of Humira treatment, and at the time of discontinuation of the treatment

12) Endoscopic examination

Date (baseline, during treatment and year 3 or after discontinuation) and endoscopic findings

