	
If all the following [1] to [4] are satisfied, aggregate the data as “160mg \rightarrow 80mg \rightarrow 40mg once every two weeks”. Others are aggregated as “others”.
 
Of note, when data on administration status include only [1], [2] and [3] or when the data ends halfway for some reason, determine whether the case satisfies the criteria from [1] to [4] as of the final data on administration status, and classify it.

Data name	Derivation and calculation methods
Administration status (total number of dosing, total dose)	
 Dosing frequency 
[1] Sort data in the order of “the first administration date” of “the administration status of Humira”, dosing frequency and description.
 
[2] Calculate the dosing interval per data on administration status. “When “once every two weeks” is checked, regard it as a 14-day interval. For others, obtain the frequency from “dosing interval”.
 
[3] Calculate the dosing frequency per data on administration status. Dosing frequency = (the final administration date (the date imputed based on the definition of 10.1 Final administration date of Humira) – the first administration date(after imputed))/dosing frequency (number of days)
 
When the results of [4] and [3] are “>0” (bigger than 0) and “<1” (smaller than 1), count it as 1.
 
If the figure is “>=1” (1 or bigger), round the decimal down to the integer for the dosing frequency.
 
[5] The total number of dosing shall be the total of [4] per patient.
 Dose 
[1] When the dose of Humira is ‘others’, obtain the dose from “Dose_other description”.
 
[2] Calculate the dose per data of the administration status.
 
Dose = the number of dosing * a dose
 
[3] The total dose should be the total of [2] per patient.
 The mean of a dose 
The mean of a dose = the total dose/the total number of dosing

Patients with self-administration	The patients whose registration form has a check on self-administration.
Age	It should be identified based on the date of birth or the first administration date of Humira in the survey form. Of note, if the “date” of birth is incomplete and not provided, impute 1 as the date. When the date of birth is still incomplete even after the above imputation, just mirror the age provided in the survey form.

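### Self-administration status is taken only from the registration form, so patients who start self-injecting after registration cannot be counted as self-injectors

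*SAP*

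**What the plan says.** **SAP 10.1, Patients with self-administration.** The whole definition is "The patients whose registration form has a check on self-administration". The survey form (the CRF) is not mentioned.

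**SAP 11, Self administration.** There are three levels: *without*, *with* and *unknown/not provided*. Nothing says how the first is told from the third.

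**Protocol 6(3)3).** The investigator completes the registration form once Humira has been chosen. As a basic rule, "we accept registration forms with a postmark date within 14 days after the date of first administration of Humira".

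**Protocol 8(2).** The registration-form list opens with "Name of institution, date of completion of the registration form, name of department, name of investigator, patient ID, patient's birthdate (year/month) or age" and goes on through treatment history, infection screening and baseline laboratory values. It allows for completion before treatment, since it asks for "date (or planned date) of initiation of Humira treatment". It contains no self-injection item.

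**Protocol 8(3)4), CRF data on treatment.** Self-injection appears here: "Patients performing self-injection: presence/absence of written consent for transition to" and then "self-injection, and presence/absence of self-injection transition record".

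**Where the status is used.** Charts 1.13 (distribution), 2.5.1 (adverse reactions, safety group), 2.5.2 (adverse reactions, patients excluded from safety analysis), 2.9 (adverse reactions by background factor, tested) and 3.4.1 (CDAI remission by background factor, tested).

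**The concern.** The SAP takes a status that can change during treatment from a form that is closed around the first dose. The protocol treats self-injection as something a patient moves to, and gives it a place on the form that is filled in every 6 months. A patient who changes in month 2 or year 2 is visible on the CRF but not to the SAP rule.

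Self-injection is a named safety interest: protocol 9(1)2) and SAP 5.1 both list administration errors during self-injection. No chart in SAP Chapter 13 is devoted to such errors, so the five charts above carry the self-injection results. If their groups are formed by status at registration but read as self-injectors against others, the comparison is mislabelled.

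**Working it through.** **1. Timing.** Latest usual registration: day 14 after the first dose (protocol 6(3)3)). Length of follow-up: first dose + 1092 days (SAP 10.1 and 12.5). Share of follow-up elapsed when status is fixed: 14 / 1092 = 1.3%. The other 98.7% cannot change it.

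**2. Source against content.**

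| Variable the SAP takes from the registration form | Counterpart in protocol 8(2)? |
|---|---|
| Contraindications (SAP 10.1) | Yes |
| Hepatitis B test status (charts 1.12, 2.9, 3.4.1) | Yes |
| Indication (charts 1.12, 2.9, 3.4.1) | Yes, as reasons for use |
| Self-administration (SAP 10.1) | No; the protocol places it on the CRF |

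The factor lists of charts 2.9 and 3.4.1 mark indication and hepatitis B as registration-form items and leave self-administration unmarked, which does not fit the SAP 10.1 definition.

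**3. Where unticked patients go.** The definition yields ticked or not ticked, while SAP 11 needs three levels. This affects the tests: SAP 9.2 and 9.5 drop *unknown/not provided* from testing but keep it in percentage denominators. Late self-injectors therefore either dilute *without* or leave the test, depending on a rule that is not written.

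**4. Size.** The plan gives no figure on self-injection to reproduce. What follows is illustration only; every input is assumed, and unticked patients are all placed in *without*.

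Let s be the share who ever self-inject and c the share of those already ticked at registration. The share of late self-injectors in the unticked group is m = s(1 − c) / (1 − sc).

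| s | c = 0.25 | c = 0.50 | c = 0.75 |
|---|---|---|---|
| 0.5 | 0.375/0.875 = 43% | 0.25/0.75 = 33% | 0.125/0.625 = 20% |
| 0.7 | 0.525/0.825 = 64% | 0.35/0.65 = 54% | 0.175/0.475 = 37% |
| 0.9 | 0.675/0.775 = 87% | 0.45/0.55 = 82% | 0.225/0.325 = 69% |

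**5. Direction.** Assume a reaction risk of 30% in patients who never self-inject and 20% in those ticked at registration.

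- *Late self-injectors also at 20%.* The true ever/never difference is 10 points. The registration rule shows 10 × (1 − m): at s = 0.5 this is 5.7, 6.7 and 8.0 points for c = 0.25, 0.50 and 0.75. The difference shrinks.
- *Late self-injectors at 30%.* The registration rule shows 30 − 20 = 10 points. At c = 0.50 the ever/never difference is 30 − (0.5 × 20 + 0.5 × 30) = 5 points. The registration rule now shows the larger difference.

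The direction depends on the risk of late self-injectors, on which the documents are silent.

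**The case against.** The registration form and CRF are protocol attachments that are not shown. The SAP is dated April 2018, after the investigation period ended in March 2017, and it speaks of a check on self-administration, so some form probably has that box. The protocol list may merely omit it. Equally, registration form may be a slip for survey form, the source the SAP uses for most derived items; then one word needs changing and nothing is misclassified. The stakes are also limited: charts 1.13 and 2.5.1 are descriptive, 2.5.2 covers only excluded patients, and in 2.9 and 3.4.1 self-administration is one of dozens of factors tested without multiplicity adjustment. Malignancy and serious-infection counts do not depend on it.

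Much of this stands, but it does not remove the point. A box on the registration form would still say nothing about later changes, and a slip still needs correcting, because the programmer follows the written source.

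It does rule out four stronger readings that a reader might infer:

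- *The* with *group will be empty.* Only if the form matches protocol 8(2) exactly, which cannot be checked.
- *Most self-injectors are misclassified.* No self-injection rate or transition timing is given.
- *The comparison is biased toward no difference.* That requires late self-injectors to carry the same risk as early ones. Those who change late have stayed on treatment long enough to do so and may differ.
- *Late self-injectors all land in* without. The undefined third level leaves this open.

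**Conclusion.** The point holds as a wrong source rule, not just a missing detail. Under SAP 10.1 as written, nobody who starts self-injecting after registration can enter the *with* group, so charts 1.13, 2.5.1 and 2.5.2 and the self-administration rows of 2.9 and 3.4.1 do not show what their labels say. This rests on two readings of the text: that SAP 10.1 means the registration form it names, and that no rule elsewhere updates the status; none was found.

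The size is unknown. Under the assumed inputs above, late self-injectors make up 20% to 87% of the unticked group, a range too wide to serve as an estimate. The direction is also unknown. The correction is worth making because it is cheap. The planned sample size is unaffected.

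**What to change.** 1. In SAP 10.1, change the source to the survey form (CRF). Class a patient as *with* if any CRF volume records self-injection, including through the consent or transition-record items. Check against the actual form how an answer of *absent* to those items should be read, because a patient may self-inject with neither document on file.
2. State the rules for *without* and *unknown/not provided*, as SAP 10.1 already does for smoking history.
3. Label charts 1.13, 2.5.1 and 2.5.2 and the rows in 2.9 and 3.4.1 as ever/never self-administration during the survey. Add a note that *with* includes reactions before the change to self-injection, and that it favours patients who stay on treatment longer.
4. Find out whether a transition date is recorded; protocol 8(3)4) does not list one. Only if it is, split both reactions and person-time by status at onset. Moving reactions alone would leave patients in the *with* denominator of chart 2.5.1 after their earlier reactions had left its numerator.

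**Cost.** Steps 1 to 3 need SAP wording and a new source variable, using items the protocol already collects. The small downside is the ever/never caveat in step 3. Step 4 costs a data check and, if a date exists, a rate-based version of chart 2.5.1.

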9.5. Statistical test method

The test does not include the classification of unknown/not provided. In principle, the first layer is subjected to the intersegmental test of classified data. Multiplicity is not adjusted.

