Indication	If multiple checkboxes such as Crohn's disease or others are selected for indication in “1. Patient information” in the survey form, count the number for each indication. Note that Crohn's disease should be selected

Data name	Derivation and calculation methods
	to display the item of indication in Attachment Form 3.
Tuberculin test	Conducted :When the first administration date of Humira is 1 and a day before the first administration date is -1, the patients who underwent Tuberculin test between -90 and 1 are regarded as the patients with Tuberculin test. Of note, the data in the survey form shall be used. Not conducted: other than the above
QuantiFeron test	Conducted: When the first administration date of Humira is 1 and a day before the first administration date is -1, the patients who underwent QuantiFeron test between -90 and 1 are regarded as the patients with QuantiFeron test. Of note, the data in the survey form shall be used. Not conducted: other than the above
Chest X ray test	Conducted: When the first administration date of Humira is 1 and a day before the first administration date is -1, the patients who underwent Chest X ray test between -90 and 1 are regarded as the patients with Chest X ray test. Of note, the data in the survey form shall be used.
Thoracic CT test	Conducted: When the first administration date of Humira is 1 and a day before the first administration date is -1, the patients who underwent thoracic CT scan between -90 and 1 are regarded as the patients with thoracic CT scan. Of note, the data in the survey form shall be used.
Imaging procedure	Conducted: When the first administration date of Humira is 1 and a day before the first administration date is -1, the patients who underwent chest X ray, thoracic CT scan, or other imaging tests between -90 and 1 are regarded as the patients with imaging test. Of note, the data in the survey form shall be used.
Tuberculosis test	The patients who underwent (Tuberculin test or QuantiFeron test) and (chest X ray, thoracic CT scan, or other imaging tests). Of note, the data in the survey form shall be used.
Patients subject to AAA measurement	Patients who are included in “CD Long AAA Measurement (final report).xlsx”.
Patients of contraindications	The patients whose registration form has at least a check on the checkbox of contraindications.
Patients who developed an infection	The patients with an infection in an external file “The priority survey item list_MedDRA20.1_FIX.xlsx”.

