Dose period	the first administration to Week 4 of administration, after Week 4 of administration to Month 3 of administration, after Month 3 of administration to Month 6 of administration, after Month 6 of administration to Year 1 of administration, after Year 1 of administration to Year 1 and Month 6 of administration, after Year 1 and Month 6 of administration to Year 2 of administration, after Year 2 of administration to Year 2 and Month 6 of administration, after Year 2 and Month 6 of administration to Year 3 of administration, Continued as of Year 3 of administration
Reason for discontinuation	Development of adverse event, lack of effectiveness, patient's wish, no visit, others
Sex	Man, women, unknown/not provided
Pregnancy/nursing	Not pregnant/nursing, pregnant, nursing, unknown/not provided
Age (in years)	<15, ≥15 and <65, ≥65, unknown/not provided
Body weight (kg)	<30, ≥30 and <40, ≥40 and <50, ≥50 and <60, ≥60, unknown/not provided
BMI(kg/m ²)	<18.5, ≥18.5 and <25, ≥25 and <30, ≥30, unknown
Duration of illness (in	<2, ≥2 and <5, ≥5 and <10, ≥10, unknown/not provided

Data	How to stratify
years)	
Indication	Crohn's disease, other, unknown/not provided
Allergy history	Without the history, with the history, unknown/not provided
Smoking history	Without the history, with the history, unknown/not provided
Details of smoking history	Smoking, only in the past (not smoking now), unknown
HBs antigen	Not conducted, conducted, unknown/not provided
Tuberculosis-test status	Not conducted, conducted
Complications	Without the history, with the history, unknown/not provided
Detailed classification of complications	Liver disorder, renal disorder, blood disorder, respiratory disorder, others
Other classification of complications	Diabetes mellitus, osteoporosis, malignant tumour, others
Medical history	Without the history, with the history, unknown/not provided
Detailed classification of medical history	Tuberculosis, non-tuberculous mycobacteriosis, interstitial pneumonia, bronchitis bacterial, aplastic anaemia, pancytopenia, malignant tumour, others
Prior medications for Crohn's disease	Without the history, with the history, unknown/not provided
Detailed classification of prior medications for Crohn's disease	Anti-TNF α drug, aminosalicylic acid products, corticosteroid, immunosuppressant, and antibiotics.
Prior treatment for Crohn's disease	Without the history, with the history, unknown/not provided

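### Tuberculosis-test status has no unknown class, so undated or blank entries count as not conducted; reading only the survey form adds a misclassification risk of unknown size

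*SAP*

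**What the plan says.** **Derivation.** SAP 10.1 defines tuberculin, QuantiFERON, chest X-ray, thoracic CT and imaging by a window around the first dose. For tuberculin, "the patients who underwent Tuberculin test between -90 and 1 are regarded as the patients with Tuberculin test". The tuberculin and QuantiFERON rows then close with "Of note, the data in the survey form shall be used. Not conducted: other than the above". The combined row needs one skin or blood test and one imaging test: "chest X ray, thoracic CT scan, or other imaging tests). Of note, the data in the survey form shall be used".

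**Levels.** The SAP 11 row "Tuberculosis-test status" has two levels, not conducted and conducted. The HBs antigen row directly above it has a third, for unknown or not provided.

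**Missing data.** SAP 9.1 imputes an unknown day for these tests to the first of the month, but sets the date to null when the month is unknown. SAP 9.2 keeps unknown/not provided in percentage denominators. SAP 9.5 takes it out of significance tests: "The test does not include the classification of unknown/not provided".

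**Collection.** Protocol 8(2) lists on the registration form "presence/absence of tuberculosis or other infection (tuberculin skin test, Quantiferon test, chest X-ray, and chest CT". The related CRF item in Protocol 8(3) is headed "Presence/absence of development of tuberculosis or serious infections" and covers "Day of examination, imaging technique, presence/absence of abnormal laboratory findings, and description of abnormal findings". It names neither tuberculin nor QuantiFERON.

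**The concern.** A two-level variable with a residual class treats absence of a usable record as evidence that nothing was done. Under these rules *not conducted* can hold patients who were not tested, patients tested on an unknown date, and patients whose entry is blank. The status is tabulated in chart 1.12, and it is tested against adverse reactions in 2.9 and against CDAI remission in 3.4.1. A mixed reference group makes the 1.12 row hard to read and would tend to dilute any real contrast in the other two.

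The choice of source could add to this. The SAP treats the two forms as distinct: it takes contraindications and self-administration from the registration form, and labels hepatitis B test status the same way. For the tuberculosis work-up it uses the survey form alone, without giving a reason, although the protocol names these tests under the other form.

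**Working it through.** The plan gives no figure for screening status, so there is nothing to reproduce. The check is on the rules.

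**Step 1: follow one skin or blood test through SAP 9.1, 10.1 and 11.**

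| Survey-form entry | Date after 9.1 | Class under 10.1 | What is actually known |
|---|---|---|---|
| Full date in Day -90 to 1 | usable | conducted | done in window |
| Month known, day unknown | first of month | decided by the imputed date | done, approximate date |
| Month unknown | null | not conducted | done, timing unknown |
| Blank | null | not conducted | nothing |
| Dated only outside the window | usable | not conducted | not done in window, on the record |

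The third and fourth lines receive a class that the record does not support.

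**Step 2: see what 9.2 and 9.5 can do.** Both act on an unknown/not provided class. HBs antigen has one, so its unknowns leave the tests. Tuberculosis-test status has none, so the third- and fourth-line patients stay in the Fisher-type comparisons of 2.9 and 3.4.1 as *not conducted*.

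**Step 3: the other rows.** The explicit residual line stands only in the tuberculin and QuantiFERON rows. For X-ray, CT, imaging and the combined status, the same result follows from the two levels in SAP 11. The combined row does not restate the window; I read it as using the windowed component rows.

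**Step 4: possible size.** The inputs are assumptions, since the documents give none. Let T be the true share with both parts done, and c the share of each part that reaches the survey form with a usable date. Assume one test per part. The apparent rate is T × c if the two parts are recorded or missing together, and T × c² if they are independent. These are two cases, not bounds. Take T = 0.90 and the registration target of 500, so 500 × 0.10 = 50 are truly unscreened.

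| c | T × c | T × c² | Expected *not conducted* of 500 |
|---|---|---|---|
| 1.0 | 0.90 | 0.90 | 50 |
| 0.9 | 0.81 | 0.729 | 500 × 0.19 = 95 to 500 × 0.271 = 135.5 |
| 0.5 | 0.45 | 0.225 | 500 × 0.55 = 275 to 500 × 0.775 = 387.5 |
| 0 | 0 | 0 | 500 |

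The error runs from none to total as c falls. The documents do not fix c.

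**The case against.** A reader might infer more: that the protocol collects screening only on the registration form, so the SAP must be counting screened patients as unscreened and understating the screening rate. The documents do not support that.

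- The CRF list in Protocol 8(3) is not exhaustive. Birth date or age, and the reason for using Humira, appear only among the registration items. Yet SAP 10.1 reads age and indication from the survey form.
- SAP 9.1 has partial-date rules for exactly these tests, which implies that dated records exist in the analysis data.
- SAP version 1.0 is dated 2 April 2018, after the investigation period ended in March 2017, so its authors could work from the forms actually used. The templates (protocol attachment c) are not in the documents.
- Protocol 8(2) lists no test dates. A Day -90 to 1 window may be workable only with survey-form dates, and treating undated registration entries as in-window could admit old tests.

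Further points also limit the concern. One missing entry need not change the combined status, because either skin or blood test, and any imaging test, will do. An unknown day alone still yields a usable date. Two-level residual coding occurs elsewhere in SAP 10.1, for example for anti-hepatitis B agents and individual prior medications, so there is no formal breach of 9.5. The documents single out tuberculosis events for stratified analysis, not screening status.

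All of this stands, and it reduces the source question to a risk that the SAP should address. It does not answer the missing class. Undated and blank entries go to *not conducted* whatever the template looks like, and the SAP does not always read a missing date as absence: a concomitant drug whose dates cannot be completed is still counted as concomitant.

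**Conclusion.** The concern holds in two parts of different strength.

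**Established from the text.** Tuberculosis-test status has no unknown level, so a test without a usable date, or a blank entry, is counted as *not conducted* and enters the tests in 2.9 and 3.4.1. For undated tests this assumes that the combined status inherits the component rows' window. How many patients are affected is not known.

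**A risk only.** The survey form is used alone although the protocol lists these tests on the registration form. Depending on the CRF template, the resulting misclassification lies anywhere from none to large, and an understated screening rate is not shown.

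The consequence is confined to one background factor. Malignancy, serious-infection and tuberculosis event counts are untouched. The change is worth making because it is cheap, not because a main result depends on it.

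**What to change.** 1. In SAP 11, add unknown/not provided to tuberculosis-test status, as for HBs antigen. Add the same level to the test rows in SAP 10.1.
2. Class a test as *conducted* if dated within Day -90 to 1; as *not conducted* if recorded as not done or dated only outside the window; and as *unknown/not provided* if blank or without a usable date. SAP 9.2 and 9.5 then apply.
3. Carry this into the combined status: *conducted* when both parts are conducted, *not conducted* when every test in at least one part is not conducted, and otherwise unknown.
4. Cross-check against the registration form. If it records a test for which the survey form has no usable date, the patient cannot be *not conducted*. Class that test as unknown/not provided, flagged as performed with date unknown, and do not assume that it fell within the 90 days.
5. State in SAP 10.1 why the survey form is the main source.

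The cost is SAP wording and one merge with data already collected. Some patients move to unknown and leave the tests in 2.9 and 3.4.1, with some loss of numbers. In chart 1.12 the *conducted* percentage stays as it is, because 9.2 keeps unknowns in the denominator; only the *not conducted* row is split. If the survey form has no way to record a test as not done, few patients will be classed as *not conducted*, so the template should be checked before the rule is finalised.
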